5.5.10.4. Multiple Comparisons/Multiplicity

In order to provide strong control of the Type I error, the key secondary analyses will be tested using a gated testing approach at a 2-sided alpha level of 0.05. If the null hypothesis is rejected for the primary endpoint, key secondary endpoints will be sequentially tested following the gatekeeping hierarchy as shown in Figure CGAW.5.2.

Following the primary objective, the sequential procedure for key secondary objectives starts with the comparison between treatment groups in the number of migraine headache days based on ITT episodic subpopulation. If the null hypothesis is rejected for that comparison, then the comparison of 50% response rate between treatment groups will be tested in the ITT population. If that null hypothesis is rejected, then the next comparison in the sequence will be tested (50% response rate in the ITT episodic subpopulation), following this same pattern until all hypotheses are tested or until the null hypothesis is accepted for an endpoint, at which point, any further testing would stop for the key secondary objectives.

Abbreviations: CM = chronic migraine patients; EM = episodic migraine patients; MHD = the number of monthly migraine headache days; MSQ RR = Migraine Specific Quality of Life Questionnaire Role Function-Restrictive domain; response = response rate. See Section 5.4 for full definitions of endpoints. Note: All testing will be conducted at a 2-sided alpha of 0.05.

Figure CGAW.5.2. Gatekeeping sequence for testing of primary and key secondary endpoints.

5.5.11. Health Outcome Analyses

All health outcome measures will be analyzed or summarized for SP III, SP IV, and SP III/IV, if appropriate.

For MSQ (total score and 3 domain scores), MIDAS (total score and item scores), MIBS-4 (total score), WPAI (4 derived scores), EQ-5D-5L (UK population-based index value, US population-based index value, and VAS score), CC

- when there are repeated measures, they will be evaluated using MMRM as described in Section 5.5.10.1.
- when there is single post-baseline measure, they will be evaluated using ANCOVA model as described in Section 5.5.1.1.

As HCRU data are count data with excess zeros for migraine patients, HCRU data will be summarized for the number of events per 100 patient years. Wilcoxon signed-rank test will be performed for comparisons within treatment group and Kruskal-Wallis test for comparisons between treatment groups.

Individual item scores of these health outcome questionnaire may be summarized if deemed necessary.

5.5.12. Safety Analyses

Unless specified otherwise, safety analyses outlined in the following subsections will be conducted on the safety population for SP III and on the GMB-treated population during the GMB-treated time; for SP III/IV, only the change from baseline with MMRM analysis will be conducted.

The safety and tolerability of treatment will be assessed by summarizing the following:

- Treatment-emergent adverse events (TEAEs)
 - o By preferred term (PT)
 - o By PT nested within system organ class (SOC)
 - o By maximum severity
 - o By considered to be related to investigational product by investigator
- Serious adverse events (SAEs) by PT
- AEs leading to discontinuation by PT
- Vital signs and weight

- Laboratory measurements
- ECGs

Additionally, TEAEs by PT will be conducted on the open-label population for SP IV only.

The baseline and postbaseline for all safety measures are described in Table CGAW.5.4 unless specified otherwise.

5.5.12.1. Categorical Safety Variables

Unless specified otherwise, the categorical safety analyses will include both scheduled and unscheduled visits.

Comparisons between treatment groups for all categorical safety measures will be made using Fisher's exact test for SP III for the safety population. Only descriptive statistics will be presented for the analyses of the GMB-treated population.

5.5.12.1.1. Adverse Events

TEAEs are defined as the reported AEs that first occurred or worsened during the postbaseline phase compared with baseline phase. For each TEAE, the severity level of the event (mild, moderate, or severe) will be determined by patient or physician opinion. The MedDRA Lowest Level Term (LLT) will be used in the treatment-emergent computation. For each LLT, the maximum severity at baseline will be used as the baseline severity. If the maximum severity during postbaseline is greater than the maximum baseline severity, the event is considered to be treatment-emergent for the specific postbaseline period.

For each patient and TEAE, the maximum severity for the MedDRA level being displayed (PT, High Level Term, or SOC) is the maximum postbaseline severity observed from all associated LLTs mapping to that MedDRA level.

For events that are sex-specific, the denominator and computation of the percentage will include only patients from the specific gender.

5.5.12.1.1.1. Potential Hypersensitivity Events

Potential hypersensitivity events (immediate and non-immediate) will be identified from a search of preferred terms generated from the following queries:

- Anaphylactic reaction (SMO 20000021)
- Broad and narrow terms in the Angioedema (SMQ 20000024)
- Broad and narrow terms in the Hypersensitivity (SMQ 20000214)

A listing of patients who reported an AE (TEAEs with all visits 1-3 as baseline, SAEs, and DCAEs) identified from these analyses will be medically reviewed to determine if the terms identified represent actual hypersensitivity events. Listings should include information on timing of event relative to latest dose of study drug administration, the event term from this query, other AEs for the patient and timing, any abnormal laboratory findings, and medical history. Only those that are judged medically to be hypersensitivity events will be included in the final tables.

The number and percentage of patients with TEAEs, SAEs, and AEs resulting in study drug discontinuation will be summarized by treatment groups using MedDRA PT nested within the SMQ. Events will be ordered by decreasing frequency within the SMQ.

The number and percentage of patients with treatment-emergent (TE) hypersensitivity events by maximum severity will be summarized by treatment groups using MedDRA PT.

The number and percentage of patients with TE hypersensitivity events by timing will be summarized using MedDRA PT. Events will be ordered by decreasing frequency. Note the timing of the hypersensitivity events is collected through eCRF and categorized into the following 4 categories:

- Immediate occurs within minutes (<60 minutes) from study drug administration.
- Acute Reaction occurs from 1 up to 6 hours from study drug administration.
- Delayed Reaction occurs from >6 hours through 14 days from study drug administration, which will be split into 2 categories: on the same day of injection and after the day of injection.
- Reaction >14 days from study drug administration.

5.5.12.1.1.2. Adverse Events Related to Injection Sites

Adverse events related to injection sites will be defined using terms from the MedDRA High Level Term "Injection Site Reactions".

The number and percentage of patients with TEAEs related to injection sites, SAEs related to injection sites, and AEs related to injection sites resulting in study drug discontinuation will be summarized using MedDRA PT. Events will be ordered by decreasing frequency.

The number and percentage of patients with TEAEs related to injection sites by maximum severity will be summarized by treatment groups using MedDRA PT.

The number and percentage of patients with TEAEs related to injection sites by timing will be summarized using MedDRA preferred terms ordered by decreasing frequency. Note the timing of AEs related to injection sites is collected through eCRF and categorized into the same categories as for hypersensitivity events.

Adverse events related to injection sites will be summarized by whether comfort measures are used and what comfort measures are used.

Follow-up forms for adverse events related to injection sites will be summarized as well.

5.5.12.1.2. Vital Signs and Weight

Vital signs collected during the study include systolic and diastolic blood pressure (SBP and DBP), pulse, and temperature. Blood pressure and pulse measurements will be taken when the patient is in a sitting position.

The number and percent of patients meeting criteria for categorical changes of interest in vital signs and weight at any time during study will be summarized. Treatment group comparisons will be performed using Fisher's exact test.

Table CGAW.5.6 displays the criteria for categorical changes of interest in vital signs and weight. The last column of the table displays the patient populations defined by baseline categories.

The criteria to identify patients with treatment-emergent abnormal changes generally consist of a combination of two parts, an absolute threshold and a change from baseline amount.

- The absolute threshold in the criteria is based on 1) minimum postbaseline when the direction is low; 2) maximum postbaseline when the direction is high.
- The change from baseline amount in the criteria is 1) decrease from baseline (defined below and in Table CGAW.5.4) to minimum postbaseline when the direction is low;
 2) increase from baseline (defined below and in Table CGAW.5.4) to maximum postbaseline when the direction is high.

The baseline for SBP, DBP, and pulse is defined as the last non-missing baseline value during the baseline period (See Table CGAW.5.4). To be exact,

- For analyses including double-blind treatment phase, the baseline for SBP, DBP, and
 pulse is defined as the last non-missing value before randomization.
 The rationale for using the last available value in the baseline period is to minimize
 the potential confound of discontinuing or dose stabilization of medications that
 modulate BP and pulse during the screening phase (which is early in the baseline
 period).
- Similarly, for GMB-treated time, the baseline is defined as the last non-missing value before patient's first dose of GMB. This baseline definition was chosen to be consistent with the analysis approach for double-blind treatment phase as described above.

This baseline definition for SBP, DBP, and pulse applies to all analyses (both continuous and categorical) for SBP, DBP, and pulse.

The baseline and postbaseline values for temperature and weight are defined in Table CGAW.5.4.

- For continuous analyses of temperature and weight, last non-missing baseline during the baseline period will be used as the baseline.
- For the analyses of categorical changes of interest in temperature and weight,
 - o the baseline is defined as the minimum value during baseline period when the direction is low.
 - the baseline is defined as the maximum value during the baseline period when the direction is high.

Table CGAW.5.6. Criteria for Categorical Changes of Interest in Vital Signs and Weight

Parameter	Direction	Criteria	Patients Population defined by Baseline Categories
Systolic BP (mm Hg)	Low	≤90 and decrease ≥20	All patients; >90; ≤90
(sitting)	High	≥140 and increase ≥20	All patients; <140, ≥140
	PCS High	≥180 and increase ≥20	All Patients; <180; ≥180
	Sustained Elevation	≥140 and increase ≥20 at 2 consecutive visits	All patients; < 140; ≥140
Diastolic BP (mm Hg)	Low	≤50 and decrease ≥10	All patients; >50; ≤50
(sitting)	High	≥90 and increase ≥10	All patients; <90; ≥90
	PCS High	≥105 and increase ≥15	All Patients; <105; ≥105
	Sustained Elevation	≥90 and increase ≥10 at 2 consecutive visits	All patients; < 90; ≥90
Systolic BP or Diastolic BP (mm Hg) (sitting)	Sustained Elevation	Meeting criteria for systolic BP for 2 consecutive visits or meeting criteria for diastolic BP for 2 consecutive visits or both	All Patients
Pulse (bpm) (sitting)	Low	<50 and decrease ≥15	All patients; ≥50; <50
	High	>100 and increase ≥15	All patients; ≤100; >100
	Sustained Elevation	>100 and increase ≥15 at 2 consecutive visits	All patients; ≤100; >100
Weight (kg)	Low	(Loss) decrease ≥7%	All patients
	High	(Gain) increase ≥7%	All patients
Temperature (° F)	Low	<96° F and decrease ≥2° F	≥96°F
	High	≥101° F and increase ≥2° F	<101°F

Abbreviations: BP = blood pressure; bpm = beats per minute; F = degrees Fahrenheit; kg = kilograms; mm Hg = millimeters of mercury; PCS= Potentially Clinically Significant.

5.5.12.1.3. Electrocardiogram Intervals and Heart Rate

Analyses of corrected QT (QTc) interval will be calculated using Fridericia's correction formula, as QT/RR $\frac{1}{3}$ (QTcF (msec)). For the QTcF calculation, the unit for QT is milliseconds and the unit for RR is seconds. For patients with QRS \geq 120 msec at any time during the study, the QT and QTc interval will be excluded from the analyses. A listing of ECG data for patients with QRS \geq 120 msec at any time during the study will be provided.

The baseline for ECG is defined as the last non-missing baseline value during the baseline period (See Table CGAW.5.4). To be exact,

• For analyses including double-blind treatment phase, the baseline for ECG is defined as the last non-missing value before randomization.

The rationale for using the last available value in the baseline period is to minimize

- the potential confound of discontinuing or dose stabilization of medications that modulate ECG during the screening phase (which is early in the baseline period).
- Similarly, for GMB-treated time, the baseline is defined as the last non-missing value before the patient's first dose of GMB. This baseline definition was chosen to be consistent with the analysis approach for the double-blind treatment phase as described above.

This baseline definition for ECG applies to all analyses (both continuous and categorical, quantitative and qualitative) for ECG.

The baseline and postbaseline values are summarized in Table CGAW.5.4.

The number and percent of patients meeting criteria for treatment-emergent abnormalities in ECG intervals (PR, QRS, and QTcF) and heart rate at any time during study will be summarized. Treatment group comparisons will be performed using Fisher's exact test.

Table CGAW.5.7 displays the criteria for treatment-emergent changes in ECG intervals and heart rate. The absolute threshold in the criteria is based on 1) minimum postbaseline when the direction is low; 2) maximum postbaseline when the direction is high.

- For treatment-emergent low analyses: Patients with all normal or high values at baseline (no low values) will be included.
- For treatment-emergent high analyses: Patients with all normal or low values at baseline (no high values) will be included.
- For treatment-emergent increase analyses: Patients with a baseline and at least 1 postbaseline result will be included.

Table CGAW.5.7. Criteria for Treatment-Emergent Changes in ECG Intervals and Heart Rate

Parameter	Direction	Criteria	
Heart Rate (bpm)	Low	<50 and decrease ≥15	
	High	>100 and increase ≥15	
PR Interval (msec)	Low		<120
	High		≥220
QRS Interval (msec)	Low	<60	
	High	≥120	
QTcF (msec)	Low	Males: <330 Females: <340	
	High	Males: >450	Females: >470
	PCS High	>500 msec	
	Increase	Increase >30 msec	
		Increase >60 msec	
		Increase >75 msec	

Abbreviations: bpm = beats per minute; ECG = electrocardiogram; msec = milliseconds; PCS = potentially clinically significant; QTcF = Fridericia's corrected QT interval.

In addition, a descriptive summary of qualitative ECG abnormalities will be conducted which will include summaries of 11 ECG categories (Axis, Rhythm, Conduction, Ischemia, Infarction, Injury, Morphology, U-waves, T-waves, ST Segment, and Other Abnormalities) of qualitative findings at any time postbaseline. A category is a collection of possible descriptions (findings) of one qualitative aspect of an ECG. A category name is the name of the qualitative aspect of the ECG (for example, Rhythm, Conduction, Morphology, Ischemia, and so forth). A finding is 1 of the possible specific descriptions (for example, Sinus Bradycardia, Acute Septal Infarction) within a category.

A shift table summary of qualitative ECGs at any time will be produced to assess shifts from baseline normal to postbaseline abnormal for the overall ECG and for each of the 11 ECG categories mentioned above.

The summaries of the 11 ECG categories will exclude ECGs with any of the following: overall ECG could not be evaluated by the cardiologist, lead reversals or <9 leads, nonmatching demographic data, and those suggesting patient identification errors.

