The primary analysis will evaluate the efficacy of galcanezumab compared with placebo on the overall mean change from baseline in the number of monthly migraine headache days during the 3-month double-blind treatment phase. Migraine headache day is defined to include both migraine and probable migraine days. The primary analysis will be performed using a restricted maximum likelihood-based mixed model repeated measures technique.

2. Schedule of Activities

Table CGAW.1. Schedule of Activities

Study Period	SP I Screening	SP II Prospective Baseline	SP III Double-Blind Treatment			SP IV Open-Label Treatment				Notes	
(Target) Interval (days) since previous visit			30-45	30	30	30	30	30	30		
Allowable range (days) between visits	3-30	30-40 ^a								ET	
Interval allowance (days)				±2	±2	±2	±2	±2	±2		
Visit	1	2	3	4	5	6	7	8	9		
Month			0	1	2	3	4	5	6		
Assessments and Procedu	res										
Informed consent	X										
Inclusion/exclusion	X	X	X								
Demographics	X										
Physical examination	X										
Neurological examination	X								X	X	
Height	X										
Weight	X		X			X			X	X	
Medical history	X										
Substance use	X										Substances: alcohol, caffeine, nicotine, tobacco
ECG	X		X			X	_		X	X	Predose and prior to blood draws. See Section 9.4.1.

Schedule of Activities

Study Period	SP I Screening	SP II Prospective Baseline	ective SP III Open-Label				Open-Label		ET	Notes	
Visit	1	2	3	4	5	6	7	8	9		
Month			0	1	2	3	4	5	6		
Vital signs	X		X	X	X	X	X	X	X	X	Includes body temperature, sitting blood pressure, and pulse. Predose and prior to blood draws. See Section 9.4.2.
Adverse events	X	X	X	X	X	X	X	X	X	X	
Concomitant medications	X	X	X	X	X	X	X	X	X	X	
ePRO and headache medication log training		X									
ePRO daily patient entries		X	X	X	X	X	X	X	X	X	
Headache medication log		X	X	X	X	X	X	X	X	X	
Patient training video			X								
Clinical Laboratory Tests	and Samplin	g Schedule									
Hematology	X		X			X			X	X	See Appendix 2.
Clinical chemistry ^b	X		X			X			X	X	Fasting is not required. See Appendix 2.
HbA1c			X			X			X	X	Fasting is not required.
Urinalysis	X		X			X			X	X	See Appendix 2. In the event of a positive urine leukocyte esterase result, a repeat urine sample will be collected and shipped to the central laboratory.

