5.5.1.5. Baseline and Postbaseline Definition

Table CGAW.5.4 describes the rules for determining the patient population and baseline and postbaseline observations for each study phase and type of analysis. When "last of Visit x-x" is used in the table, the last non-missing observation obtained in the visit interval will be used.

Table CGAW.5.4. Patient Population with Baseline and Postbaseline Definitions by Study Period and Type of Analysis

Study Period/Analysis	Patient Population	Baseline Observation	Postbaseline Observation(s)		
Study Period III					
Efficacy analyses (Repeated measures) or average of observed monthly values		Visit 3	All scheduled visits 3 < Visits ≤6		
Efficacy analyses at LOCF endpoint	ITT population and ITT episodic sub-population	Visit 3	Last of Visit 3.01–6		
Health outcome analyses (Repeated measures)	with a baseline and at least 1 postbaseline observation	Visit 3	All scheduled visits 3 < Visits ≤6		
Health outcome analyses at LOCF endpoint or for average of observed monthly values		Visit 3	Last of Visit 3.01-6		
Treatment-emergent adverse events	Safety population	All Visits 1–3*a	All Visits 3.01–6		
Serious adverse events, discontinuations due to adverse events	Safety population	NA	All Visits 3.01–6		
Treatment-emergent abnormal laboratory values	Safety population with normal (with respect to direction being analyzed) laboratory values at all non-missing baseline visits and who have at least 1 postbaseline observation	Low: Min of Visits 1–3 High: Max of Visits 1–3 Abnormal: All Visits 1–3	Low: Min of Visits 3.01–6 High: Max of Visits 3.01–6 Abnormal: All Visits 3.01–6		
Treatment-emergent changes in temperature and weight	Safety population with a baseline and at least 1 postbaseline observation	Low: Min of Visits 1–3 High: Max of Visits 1–3	Low: Min of Visits 3.01–6 High: Max of Visits 3.01–6		
Treatment-emergent changes in blood pressures, pulse, and ECGs	Safety population with a baseline and at least 1 postbaseline observation	Low: Last of Visits 1–3 High: Last of Visits 1–3	Low: Min of Visits 3.01–6 High: Max of Visits 3.01–6		
Continuous safety analyses (Repeated Measures)	Safety population with a baseline and at least 1 postbaseline observation	Last of Visits 1–3	All scheduled visits 3 < Visits ≤6		
Continuous safety analyses – change from baseline to LOCF endpoint (ANCOVA)	Safety population with a baseline and at least 1 postbaseline observation	Last of Visits 1–3	Last of Visits 3.01–6		

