5.5.12.2. Continuous Safety Measures

Analyses of continuous safety data will be conducted for SP III and SP III/IV on patients who have a baseline and at least 1 postbaseline observation. In those analyses, values from

unscheduled visits will not be included, and only values collected at scheduled visits will be used.

For continuous safety measures (including laboratory measures, vital signs and weight, ECG intervals and heart rate), changes from last baseline value to LOCF endpoint during SP III, will be assessed using an ANCOVA model with treatment and baseline value as covariates. If repeat laboratory values exist at the same scheduled visit, only the last non-missing laboratory value at a visit (selected by using the variable with highest lab sequence ID) will be used in the ANCOVA analysis for mean change from last baseline value to LOCF endpoint.

For vital signs of blood pressure and pulse rate, as well as weight (when applicable), the mean change from baseline will be analyzed for SP III and SP III/IV using an MMRM analysis. The analysis will include the fixed categorical effects of treatment, month, and treatment-by-month interaction, as well as the continuous fixed covariates of baseline value and baseline-by-month interaction.

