5.8.1.2. Report to be Generated at Final Database Lock

All reports that have not been generated as part of the interim analyses or that did not contain final data at the time of the interim analysis (i.e., any reports based on SP IV or SP III/IV) will be generated at final database lock. Reports from the double-blind treatment period will be final at the interim analysis and therefore will not be rerun for the final database lock.

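### The QRS rule drops all of a patient's QT/QTc data for one wide-QRS ECG at any time, so an open-label ECG can remove a patient from the double-blind QTcF comparison and the analysed set depends on the lock date

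*SAP*

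**What the plan says.** SAP 5.5.12.1.3 sets the QTcF method and then a restriction: when a patient has QRS of 120 msec or more "at any time during the study, the QT and QTc interval will be excluded from the analyses". It gives no reason and adds one output: "A listing of ECG data for patients with QRS" at or above that limit. Protocol 10.3.4.3 plans the QTcF analysis without any QRS exclusion.

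The restricted data feed two between-arm comparisons in SP III:

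- **Categorical (SAP 5.5.12.1):** "Comparisons between treatment groups for all categorical safety measures will be made using Fisher's exact test for SP III for the safety population". Table CGAW.5.7 lists the QTcF categories: low, high, above 500 msec, and increases above 30, 60 and 75 msec.
- **Continuous (SAP 5.5.12.2):** "For continuous safety measures (including laboratory measures, vital signs and weight, ECG intervals and heart rate"), an ANCOVA of change from the last baseline value to the LOCF endpoint in SP III, using scheduled visits only.

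Table CGAW.5.7 also makes QRS of 120 msec or more the treatment-emergent high category for QRS itself.

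On timing, SAP 5.8.1.1 produces all SP III analyses at the interim lock, together with several SP IV outputs. SAP 5.8.1.2 adds: "Reports from the double-blind treatment period will be final at the interim analysis and therefore will not be rerun for the final database lock".

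**The concern.** Whether a patient counts in a randomised QTc comparison should be settled by data from before dosing, or at most by recordings from the period being compared. Here it can be settled by an ECG taken after everyone still in the study has moved to galcanezumab. A patient randomised to placebo whose QRS is wide on open-label galcanezumab would leave the placebo arm of the double-blind QTcF tables. An otherwise identical patient enrolled later, whose open-label ECG had not been taken by the lock, would stay.

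The rule also costs valid data. QTc is hard to interpret on a recording with a wide QRS. That is a reason to set that recording aside, not the same patient's recordings with normal QRS.

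At stake are the denominators, and possibly the rare events, of a secondary safety comparison.

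**Working it through.** No stated figure in the plan rests on this rule, so the check is mainly of the text.

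**Step 1. Which ECGs exist.** The Schedule of Activities (Protocol Section 2) places ECGs at Visits 1, 3, 6 and 9 and at early termination (ET), before dosing. The Visit 6 ECG therefore precedes the first open-label injection and belongs to SP III. SP III has one scheduled postbaseline ECG (Visit 6, or ET). SP IV has one (Visit 9, or ET).

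**Step 2. Whether anything narrows the rule.** The Table CGAW.5.4 row "Treatment-emergent changes in blood pressures, pulse, and ECGs" limits SP III observations to the last of Visits 1–3 for baseline and Visits 3.01–6 for postbaseline. It bounds which values are analysed, not which patients the QRS rule removes. No other section limits the rule.

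**Step 3. Whether SP IV ECGs can be in the database at the interim lock.** Visit 9 follows Visit 6 by three intervals of 30 ± 2 days: 3 × 28 = 84 to 3 × 32 = 96 days. Patients whose Visit 6 fell about that long before the lock, or who left SP IV early, can have an SP IV ECG by then. SAP 5.8.1.1 plans SP IV exposure, disposition and adverse-event outputs at this lock, so SP IV data are expected to be present.

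**Step 4. The rule as written against a filter on single recordings within the analysis period.** Each row assumes normal QRS at all other visits.

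| Only wide-QRS ECG | SP III QTcF tables, as written | SP III QTcF tables, recording-level |
|---|---|---|
| Visit 9, in the database at the lock | removed | kept in full |
| Visit 9, after the lock | kept (tables not rerun) | kept in full |
| Visit 1 | removed | kept; Visit 3 is the baseline |
| Visit 3 | removed | kept; Visit 1 is the last usable baseline |
| Unscheduled, in SP III | removed | kept; Visit 6 remains |
| Visit 6 (or ET in SP III) | removed | still removed unless a usable unscheduled ECG exists (categorical tables only) |

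The first two rows have the same SP III data and differ only in the lock date, yet the rule as written treats them differently.

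In galcanezumab-treated time, a patient randomised to galcanezumab has scheduled postbaseline ECGs at Visits 6 and 9. One wide QRS at either visit discards both; a recording-level filter keeps the other.

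**Step 5. Size.** The documents give no rate of wide QRS, so the following is assumption only. With 420 patients, any-visit rates of 0.5%, 1%, 2% and 5% give 420 × rate = 2.1, 4.2, 8.4 and 21 patients. These counts include wide QRS present before dosing. The part that depends on the lock is smaller and cannot be derived. One patient is 1/210 = 0.5% of an arm.

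**The case against.** The strongest reply has four parts.

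**The phrase may be meant within a period.** The same SAP section counts treatment-emergent abnormalities at any time during the study, and Table CGAW.5.4 confines those counts to the relevant visits. That reading is possible and may be what the sponsor intends, but the text does not say it. Even on that reading the rule still removes patients rather than recordings.

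**Filtering recordings changes little in the main case.** This stands. SP III has a single scheduled postbaseline ECG, so a patient whose QRS is wide there leaves the SP III QTcF tables under either rule. The gain lies in the other rows of the comparison.

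**A reader might infer that the rule hides a safety signal.** The documents do not support that. A patient with emergent QRS widening is still counted in the QRS high category (if baseline QRS was not high), appears in the qualitative ECG summaries and shift table, which include conduction, and is in the dedicated listing. The direction of any bias in QTcF is unknown. One can construct an example: 6/210 against 0/210 gives a Fisher p of 0.030, and 4/208 against 0/210 gives 0.060 after two removals. But this places a third of the events in patients with wide QRS. If those values came from the wide-QRS recordings, the better filter would remove them too. The p-value is also fragile: 4/210 against 0/210 gives 0.123.

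**A reader might infer that the SP III population is undefined.** It is not. The safety population is defined, a locked database gives one result, and findings after the lock cannot alter the SP III reports. The accurate description is that the QTc set depends on the lock date.

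**Conclusion.** The concern holds in a limited form. As written, SP IV recordings present at the interim lock can remove patients, including those randomised to placebo, from the final SP III QTcF comparison, although their SP III ECGs were all usable. The rule also discards valid QTc values after a single wide QRS at screening, at an unscheduled visit, or elsewhere in galcanezumab-treated time. This follows from the wording and rests on no assumed rate.

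The number of patients is not given and is probably small. The effect is confined to QT/QTc safety outputs; primary and key secondary efficacy results do not change. The change is worth making because it is nearly free. It also brings the rule into line with the section's own qualitative ECG summaries, which exclude individual unusable ECGs rather than patients.

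**What to change.** Replace the sentence in SAP 5.5.12.1.3 with a rule on recordings: QT and QTc are excluded only for the individual ECGs with QRS of 120 msec or more, and the filter is applied only to ECGs within the analysis period. For SP III that means baseline through the predose Visit 6 or ET ECG. State that baseline is then the last non-missing usable value. Keep the planned listing. Report by arm how many patients leave the SP III QTcF tables because their only postbaseline ECG had a wide QRS.

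The cost is one SAP sentence, a filter in the ECG analysis program and one extra count. The downside is that a few patients contribute fewer ECGs, and those with a wide QRS at their only SP III postbaseline ECG are still not analysed for QTcF in that period.
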